## 2.2. Schedule of Events

Table 2-1: Schedule of Events

Assessment/Evaluation	Study Periods					
	Visit 1	Visit 2	Visit 3	Visits 4 to 13	Visit 14 / ET	Visit 15
	Screening	Baseline	1st Month	Monthly	End of Treatment	Follow-up
	[REDACTED]	[REDACTED]	[REDACTED]	[REDACTED]	[REDACTED]	[REDACTED]
Informed Consent Form	X a	X a				
Subject Demographics	X					
Urine Drug Screen	X	X	X	X	X	
Pregnancy Test b	X	X	X	X	X	
MINI 7.0.2	X					
Medical and Psychiatric History	X					
Record Concomitant Medication Use	X	X	X	X	X	
[REDACTED]	[REDACTED]					
LSAS	X	X	X	X	X	
HAM-D17 [REDACTED]						
C-SSRS	X	X	X	X	X	X
Physical Examination c,d	X	X	X	X	X	
Vital Signs	X	X	X	X	X	X
12-Lead Electrocardiogram e	X	X	X	X	X	
Clinical Chemistry, Hematology, and Urinalysis	X	X	X	X	X	
Review Inclusion/Exclusion Criteria	X	X f				
CGI-S	X	X	X	X	X	
CGI-I			X	X	X	
PGI-C			X	X	X	
PWC-20					X	X

Assessment/Evaluation	Study Periods					
	Visit 1	Visit 2	Visit 3	Visits 4 to 13	Visit 14 / ET	Visit 15
	Screening	Baseline	1st Month	Monthly	End of Treatment	Follow-up
	Day -35 to Day -7	Day 0	Day 30 ±3 days	±7 days	52 Weeks ±2 weeks	54 Weeks ±3 days
Training on Use of PH94B		X				
Storage Instructions		X	X	X		
Training on eDiary App to Record PH94B Use and Health Problems		X				
Adverse Event Recording		X	X	X	X	X
Dispense PH94B to Subject		X	X	X		
eDiary Review			X	X	X	

Abbreviations: C-SSRS = Columbia-Suicide Severity Rating Scale; CGI-I = Clinical Global Impression Scale of Improvement; CGI-S = Clinical Global Impression Scale of Severity; eDiary = electronic diary; ET = Early Termination; HAM-A = Hamilton Rating Scale for Anxiety; HAM-D17 = Hamilton Rating Scale for Depression (17 items); LSAS = Liebowitz Social Anxiety Scale; MINI = Mini-International Neuropsychiatric Interview; PGI-C = Patient Global Impression of Change; PWC-20 = Penn Physician Withdrawal Checklist; SAD = social anxiety disorder

- a Subjects will sign an informed consent form for the present study at either Visit 1 or Visit 2, depending on when they enter the study.
- b Pregnancy tests will only be given to female subjects of childbearing potential and not post-menopausal females.

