Subjects will be instructed to return to the clinic for Visit 3 after 30 days ( $\pm 3$  days). At Visit 3, subjects will undergo clinical laboratory assessments (clinical chemistry, hematology, urinalysis, pregnancy test, and urine drug screening), vital signs, 12-lead ECG, physical examination (limited to nasal passage and oropharynx examination unless any AEs are reported), HAM-D17, [REDACTED] LSAS, C-SSRS, CGI-S, CGI-I, and self-evaluation by the patient-reported outcome measure, Patient Global Impression of Change (PGI-C). At Visit 3, PH94B use and any daily reports of health problems that have been recorded in the eDiary application will be reviewed and AEs and concomitant medications will be reported and recorded. Subjects will receive a 1-month supply of PH94B.

Subjects will return to the clinic at monthly intervals ( $\pm 7$  days, Visits 4 to 13), and will repeat the same assessments as those performed at Visit 3. PH94B use and any daily reports of health problems that have been recorded in the eDiary application will be reviewed, AEs and concomitant medications will be reported and recorded at each visit. Subjects will receive a 1-month supply of PH94B at each monthly visit.

At Visit 14 (12 months $\pm$ 2 weeks), treatment will conclude, and subjects will undergo clinical laboratory assessments (clinical chemistry, hematology, urinalysis, pregnancy test, and urine drug screening), vital signs, 12-lead ECG, physical examination, HAM-D17, [REDACTED] LSAS, C-SSRS CGI-S, CGI-I, PGI-C, and the Penn Physician Withdrawal Checklist (PWC-20). Also, PH94B use and any daily reports of health problems that have been recorded in the eDiary application will be reviewed, and AEs and concomitant medications will be recorded and reported. Subjects will also be informed of their follow-up visit (Visit 15).

Subjects will return to the clinic for a follow-up visit (Visit 15, 54 weeks  $\pm$ 3 days), approximately 2 weeks after the last PH94B administration, to undergo C-SSRS, PWC-20, and vital signs assessments, and record AEs.

Subjects who discontinue study treatment without completing 12 months of treatment will attend an Early Termination Visit (Visit 14) as soon as possible after discontinuing treatment, and return to the clinic for a follow-up visit (Visit 15) approximately 2 weeks later.

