### **9.10. Drug Accountability**

Upon receipt of each IP shipment, an inventory must be performed, and a drug receipt log filled out and signed by the person accepting the shipment. The IP will be provided with each vial assembled individually to its spray actuator. It is important that the designated study staff count and verify that the shipment contains all the items noted in the shipment inventory. Any damaged or unusable IP in each shipment (active drug) will be documented in the study files.

Current and accurate inventory and dispensing records will be kept for all IP. Upon study completion a final inventory of all clinical supplies will be compiled. The Investigator or an assistant will instruct subjects to return spray vials to the clinical site, whether empty or containing unused IP, at study visits prior to subjects receiving additional supplies of IP. A copy of the Drug Receipt Form and the Drug Accountability Form will be retained in the Investigator's files.

If the subject reports the IP as being lost or stolen this will be recorded in the eCRF.

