### **10.2.2 Treatment Period**

#### **10.2.2.1 Visit 2 (Baseline)**

Subjects entering the study within 14 days of their antecedent PH94B SAD study will enter this study at Visit 2. These subjects will sign an ICF for the present study at this visit and complete all Visit 2 assessments as noted in the schedule of events (Table 2-1) and detailed in this section.

All subjects will complete the following Visit 2 assessments:

- Obtain urine sample for urine drug screen: Instant Exam to be performed on site, with results thoroughly documented in the source; urine samples will be sent to the central laboratory for confirmation as needed if on-site urine drug screen is positive. If the central laboratory urine drug screen result is positive [REDACTED]

[REDACTED], the subject may have to be excluded from the study; the Medical Monitor should be consulted on these cases

- For females of childbearing potential, obtain urine sample and complete on-site urine pregnancy test
- Record concomitant medication use
- Perform physical examination, including body weight (pounds). The physical examination includes a review of the nasal passages
- Measure vital signs after the subject has rested for 5 minutes: seated systolic and diastolic blood pressure, heart rate, respiratory rate, and body temperature (°F)
- Obtain 12-lead ECG in supine position after the subject has rested for 5 minutes
- Obtain blood and urine samples for evaluation by the central clinical laboratory, including hematology, chemistry, thyroid functioning, and urinalysis
- Review all inclusion and exclusion criteria

For subjects meeting all study inclusion criteria and no study exclusion criteria, the following Visit 2 procedures will be performed:

- Administer the LSAS
- Administer the HAM-D17
- [REDACTED]
- Administer the C-SSRS (Since Last Visit)
- Complete the CGI-S with a recall period of 1 week (by the trained clinician)
- Train subjects on the use, dosing, and storage of IP. The subject will be given instructions on:
  - how to position the actuator nozzle in the nasal passages and self-administer IP
  - the number of sprays per nostril per dose (1 per nostril)
  - how to store the nasal spray
  - Treatment with PH94B should be self-administered approximately 15 minutes prior to or during an anxiety-provoking social situation or event. [REDACTED]  
[REDACTED], with no more than 4 administrations per day. Treatment does not need to be administered every day.

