#### **10.2.3 Visit 14 End of Treatment (or Early Termination) Visit**

At Visit 14, subjects should return to the study site for an End of Treatment visit, and undergo the assessments shown in the schedule of events.

In addition, subjects who discontinue from the study early (for any reason other than loss to follow-up) should return to the study site for an Early Termination Visit. Similarly, if the subject is attending a scheduled visit when the decision to discontinue is made, the investigator should perform the assessments indicated for Visit 14/Early Termination Visit in the schedule of events (Table 2-1).

The following assessments will be completed at Visit 14/Early Termination:

- Record concomitant medication use
- Obtain blood and urine samples for evaluation by the central clinical laboratory, including hematology, chemistry, thyroid functioning, and urinalysis (refer to Section 10.3.1.1.1 for complete list)
- Conduct urine drug screen (Instant Exam, to be performed on site, with results documented in the source. If urine drug screen result is positive [REDACTED], then then urine sample will be sent to central laboratory for confirmation as needed).
- For females of childbearing potential, obtain urine sample and complete on-site urine pregnancy test
- Obtain 12-lead ECG in supine position after the subject has rested for 5 minutes
- Perform physical examination, including height (inches) and body weight (pounds). Also includes an examination of the nasal passages
- Measure vital signs after the subject has rested for 5 minutes: seated systolic and diastolic blood pressure, heart rate, respiratory rate, and body temperature (°F)
- Administer the LSAS
- Administer the HAM-D17
- [REDACTED]
- Administer the C-SSRS (Since Last Visit)
- Complete the CGI-S with a recall period of 1 week (by the trained clinician)

- Complete the CGI-I as compared to baseline visit (Visit 2), with a recall period of 1 week (by the trained clinician)
- Complete the PGI-C as compared to baseline visit (Visit 2), with a recall period of 1 week (by the subject)
- Complete PWC-20
- Review the use of IP and any health problems they experienced as reported in the eDiary (by the trained clinician)
- Review and record AEs (by the trained clinician)

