6.1. Statistical Definitions and Algorithms

6.1.1. Baseline

The last observation recorded before the first dose of PH94B will be used as the baseline observation for all calculations of change from baseline.

Table 1: Baseline Definitions

Parameter	Baseline
Safety Variables (clinical laboratory assessments, vital signs, ECGs, physical examinations)	The last non-missing assessment before the first dose of study drug given at Visit 2 (Baseline).
C-SSRS Scores	Scores on the Baseline version of the C-SSRS given at Visit 1 (Screening).
LSAS total score, HAM-D total score, [REDACTED]	Total score at Visit 2 (Baseline).

Abbreviations: CGI-I = Clinical Global Impression of Improvement; ECG = electrocardiogram; C-SSRS = Columbia-Suicide Severity Rating Scale; [REDACTED] HAM-D = Hamilton Depression Scale; LSAS = Liebowitz Social Anxiety Scale

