8.9. Coronavirus 2019 (COVID-19) Impact

The SARS-CoV-2 virus and variants may still be a threat and safety precautions may still be in place during study enrollment. To assess the impact of the COVID-19 pandemic on study

AD-ST-33.06 Effective date: 12-Nov-2020

procedures, study staff will complete the COVID-19 Impact questionnaire. Should a study Visit be affected by COVID-19, study staff will record how the Visit was affected (missed, abbreviated, delayed, performed remotely, or otherwise deviating from the planned format in the protocol) and which procedures were impacted. All COVID-19 protocol deviations will be provided in a separate listing. This listing will include the subjects, affected Visits, and affected assessments.

10. Changes from Planned Analysis

Endpoints removed: analysis not performed – data not collected.

Study staff will complete the Coronavirus 2019 (COVID-19) Impact questionnaire to assess the impact of the COVID-19 pandemic on study procedures. The COVID-19 Impact questionnaire is described in Section [8.9](#). All COVID-19 protocol deviations will be provided in a separate listing.

Exploratory objectives (changes in pattern of PH94B use daily frequency and dosing interval) requiring the use of eDiary data were removed due to unreliability of eDiary data.

The original planned interim safety analysis was removed from the study.

A qualitative review of categorical data was done instead of an assessment of a change in proportion over time due to limited availability of data.

11. References

ASA. (2018) Ethical Guidelines for Statistical Practice. Prepared by the Committee on Professional Ethics, April 2018. <http://www.amstat.org/about/ethicalguidelines.cfm>

Carpenter JR and Kenward MG. *Multiple Imputation and its Application (Statistics in Practice)*. Chichester, West Sussex, UK: John Wiley & Sons; 2013.

Graham JW, and Olchowski AE, Gilreath TD. (2007) “How Many Imputations are Really Needed? Some Practical Clarifications of Multiple Imputation Theory.” *Prev Sci.* 2007;8(3): 206-213.

ICH (1998). ICH Harmonised Tripartite Guideline. Statistical Principles for Clinical Trials E9; 1998. https://database.ich.org/sites/default/files/E9_Guideline.pdf

Little R and Rubin D. (1987). Statistical Analysis with Missing Data, New York: Wiley.

RSS. (2014) The Royal Statistical Society: Code of Conduct, 2014. <https://rss.org.uk/about/policy-and-guidelines/code-of-conduct/>.

12. Tables, Listings, and Figures

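### No listed visit procedure dates the first or last as-needed dose, so time off drug at the PWC-20 cannot be reliably derived

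*Protocol*

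**What the plan says.** Withdrawal symptoms are part of the protocol's primary objective (Section 6.1), and PWC-20 scores after stopping PH94B are a safety endpoint in both documents (Protocol 6.3, SAP 2.2.1). The checklist is given at Visit 14/ET and Visit 15. Protocol 10.3.1.2.5 says its questions concern the week after discontinuation.

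Dosing is discretionary: "Treatment does not need to be administered every day" (Protocol 10.2.2.1). Visit 15 is described in Section 7.1 as "approximately 2 weeks after the last PH94B administration, to undergo C-SSRS, PWC-20, and vital signs assessments". Table 2-1 puts Visit 14 at "52 Weeks ±2 weeks" and Visit 15 at "54 Weeks ±3 days". Section 10.1 instead counts 2 weeks from the last visit. For early terminators, Section 7.1 counts about 2 weeks from the Early Termination visit, which itself follows the stop of treatment.

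Neither the schedule nor the lists for Visits 2, 3, 14 and 15 include a first-dose or last-dose date. At Visit 14/ET the item on use is "Review the use of IP and any health problems they experienced as reported in the eDiary (by the trained clinician". The eDiary takes daily dose counts and approximate times (Protocol 9.4.1). SAP Section 10 reports that exploratory objectives "requiring the use of eDiary data were removed due to unreliability of eDiary data".

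The SAP nevertheless relies on dose dates. Baseline for safety variables is "The last non-missing assessment before the first dose of study drug given at Visit 2 (Baseline" (SAP 6.1.1). Treatment-emergent AEs begin at the start of IP (8.1). Partial onset dates and times are imputed from the date and time of first dose (6.1.8). Serious TEAEs are split at IP administration at Visit 2 (8.1.2). Days of exposure are the Visit 14 date minus the Visit 2 date (6.1.7.1). PWC-20 is summarised for subjects who completed both Visits 14 and 15 (8.7), with no variable for time off drug.

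**The concern.** A withdrawal checklist can be read only against the time since the drug was last taken. With scheduled daily dosing, the end-of-treatment visit fixes that time closely enough. With as-needed use it does not: the last dose may be on the day of Visit 14 or weeks before it. A subject who has not dosed for some time gives an off-drug score at Visit 14, so the comparison of Visit 14 with Visit 15 no longer contrasts on-drug with off-drug. Pooling such subjects with recent users could hide a withdrawal signal confined to recent users, and the report could not show whether it had.

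The first dose has a smaller version of the same problem. The SAP writes as though it were given at Visit 2, while the protocol's Visit 2 trains the subject and dispenses a kit. No source is named for the first-dose date that the TEAE and imputation rules need.

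**Working it through.** **1. The plan's own figure.** Visit 14 is day 52 × 7 = 364, ±14. Visit 15 is day 54 × 7 = 378, ±3. The nominal gap is 378 − 364 = 14 days. This reproduces the stated 2 weeks, on condition that the last dose is taken on the day of Visit 14 and both visits are on target.

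**2. What the windows allow.** Earliest Visit 15 minus latest Visit 14 is 375 − 378 = −3 days; latest Visit 15 minus earliest Visit 14 is 381 − 350 = 31 days. The negative end means only that the windows overlap. As the visits run in order, the gap can be 0 to 31 days.

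**3. Adding as-needed use.** Let the last dose fall d days before Visit 14. The documents give no value for d, so these are assumptions. Time off drug is d at Visit 14 and 14 + d at a nominal Visit 15; within the windows it is d to d + 31.

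| d (days, assumed) | Off drug at Visit 14 | Off drug at nominal Visit 15 | Visit 15 within windows |
|---|---|---|---|
| 0 | 0 | 14 | 0 to 31 |
| 7 | 7 | 21 | 7 to 38 |
| 14 | 14 | 28 | 14 to 45 |
| 28 | 28 | 42 | 28 to 59 |

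From d = 7 upward, the week after the last dose, which the checklist is meant to cover, has ended by Visit 14.

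**4. Whether vial weights can supply d.** Vials are weighed at dispensing and return, and the weights go into the eCRF (Protocol 9.4). The SAP derives use from them by visit (6.1.7.1). A weight loss in the last kit shows use somewhere between Visit 13 and Visit 14. With 30-day months, Visit 13 is day 30 + 10 × 30 = 330. The interval is then 364 − 330 = 34 days nominally, from 350 − 337 = 13 to 378 − 323 = 55 within the windows. Weights therefore confirm use in an interval but do not date it.

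**5. First dose.** A first dose from the first kit can fall from day 0 to day 33 (Visit 3 at day 30 ±3). Days of exposure count from Visit 2 wherever in that range it falls.

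**6. Illustration of possible dilution.** Assume doses occur at random at one common rate of r per week. The share with no dose in the 7 days before Visit 14 is exp(−r): 61% at r = 0.5, 37% at 1, 14% at 2 and 0.1% at 7. If, as a further assumption, withdrawal symptoms arose only in subjects who dosed in that week, the pooled rate would be 1 − exp(−r) of the rate in those subjects: 39%, 63%, 86% and 99.9%. No use rate stands in the documents, so this shows the shape of the effect, not its expected size.

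**The case against.** The strongest reply is that more is recorded than the visit lists suggest. Vial weights are in the eCRF. The SAE form asks for first- and last-dose dates (Protocol 11.2.6.1). Withdrawn subjects have a discontinuation date (8.3). The eCRF pages are not among the documents, and SAP 6.1.8 presupposes a first-dose variable. This stands in part: one cannot say that the eDiary is the only dosing record, or that no form holds a dose date. But weights carry no date, the SAE form covers only SAE cases, and the discontinuation date is not defined as the last dose.

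Second, SAP Section 10 drops objectives on frequency and dosing interval and does not mention dose dates. True, but the stated reason is that the eDiary data are unreliable, and a dose date would come from the same entries.

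Third, the all-subject PWC-20 result is a fair description of stopping after as-needed use, and rare users have little to withdraw from. That stands, and is why a display by recency should sit beside it, not replace it.

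A reader might also infer three stronger points that the documents do not support:

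- **AEs before first use are counted as treatment-emergent.** The SAP anchors TEAEs at the start of IP without naming a source. Use of Visit 2 is only suggested by Sections 6.1.1 and 8.1.2, and any error would be toward over-counting.
- **The final kit is neither weighed nor returned.** Protocol 9.10 does tie vial return to "at study visits prior to subjects receiving additional supplies of IP", dispensing ends at Visit 13, and the Visit 14/ET list has no collection step. But weighing on return (9.4), the final inventory (9.10) and the SAP's weight formula imply return. This is a missing instruction only.
- **Baseline should move to the actual first dose.** Protocol 13.1.2.3 sets baseline at Visit 2 for everyone, and for anyone first dosing before Visit 3 the last scheduled assessment before that dose is Visit 2 in any case.

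**Conclusion.** The point holds for data capture. On the listed procedures, time off drug at the Visit 14 and Visit 15 PWC-20 is unknown, and the nominal 2 weeks is correct only when the last dose coincides with Visit 14. The visit windows alone allow a gap of up to 31 days, and as-needed use adds an undated interval before Visit 14. The pooled summary therefore cannot separate an absence of withdrawal symptoms from an absence of recent use.

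This rests on two assumptions: that the listed procedures reflect what is collected, and that eDiary entries judged unreliable for patterns of use are also unfit for dating doses. How far the PWC-20 result is diluted cannot be stated, because it depends on use rates that the documents do not give. The first-dose issue is smaller: an unnamed source, and SAP wording about a first dose at Visit 2 that must be reconciled with the protocol's Visit 2 procedures.

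**What to change.** 1. At Visit 14/ET, have staff record the date of last dose and the number of dosing days in the past 7. At Visit 15, record any use since Visit 14/ET, with its date.
2. Show PWC-20 at Visits 14 and 15 by recency of last dose, beside the all-subject summary.
3. Record the first-dose date at the first visit after use. Name it in the SAP as the source for the TEAE start and the Section 6.1.8 imputation, and keep baseline at Visit 2. Reconcile the SAP's wording on the first dose with Protocol 10.2.2.1.
4. Reconcile the protocol's descriptions of when Visit 15 falls, and state in the Visit 14/ET list whether vials are returned and weighed there.

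If data collection is over, the SAP should still name its first-dose source and state that time off drug at PWC-20 is unknown.

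The cost is a few eCRF fields at existing visits and one extra display. The drawback is recall: about a month back for a first dose early in the first kit, and for the last dose however long before Visit 14 it was taken. Vial weights can confirm use in the interval but not the date.

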#### Safety Considerations:

Safety and tolerability of PH94B ( $\leq$  4 doses per day up to 12 months in up to 600 subjects) will be assessed and summarized through changes from baseline (Visit 2) to end of treatment (Visit 14) in AEs, laboratory values, 12-lead ECGs, physical examinations, suicidality, level of depression, vital sign assessments, and withdrawal symptoms following exposure to PH94B.

### **7.2. Rationale and Discussion of Study Design**

The present study has been designed to evaluate the safety and tolerability of PH94B with repeated dosing over a period of up to 12 months, in subjects who have participated in previous PH94B SAD studies. Participating subjects will use PH94B up to 4 times a day when they encounter anxiety-provoking social situations in daily life. Formal evaluation of the efficacy of PH94B is being conducted in 2 Phase 3 studies, which have been designed and powered to assess its efficacy in reducing anxiety in a public speaking challenge. In the present study, evaluation of the efficacy of PH94B over the 12-month treatment period is an exploratory objective.

Given that evaluation of long-term safety is the primary objective of this study, an open-label study with no comparator is considered to be an appropriate design.

Safety assessments in this study are standard for the evaluation of an investigational medicinal product, and include collection of AEs and SAEs, and evaluation of vital signs, safety laboratory tests, 12-lead ECGs, and physical examinations; given the use of the i.n. route of administration, the physical examination will include an examination of the nasal passages. Given that subjects are patients with a confirmed diagnosis of SAD, the C-SSRS will be used at each study visit as a precautionary measure. Withdrawal symptoms will also be assessed.

The exploratory evaluation of efficacy of PH94B with long-term use will use clinician-rated tools such as the LSAS, CGI-I and CGI-S, and a patient-reported outcome measure, the PGI-I. These are commonly used in clinical studies of psychiatric disorders, including SAD, and are considered appropriate for the present study.

